Hospital:	The Queen Elizabeth and Royal Adelaide Hospitals, Central Adelaide Local Health Network
Study Question:	Does a transitional model of care using a telehealth intervention decrease hospital readmission in patients with multimorbidity
Study Aim:	The aim of this study is to develop and test a transitional model of care to optimally support people living with multimorbidity, post-hospital discharge, via telehealth, and ensure continuity of care between the secondary (acute) and primary healthcare sectors to minimise direct contact with hospital services
Primary Objectives:	1. Assess impact of intervention on 1 month readmission post- discharge
Secondary Objectives	
 1. Calculate a cost analysis on the transitional service model of care 2. Evaluate the patient experience with continuity of care and the transition service 3. Assess patients' symptom burden pre and post transitional support service intervention 4. Evaluate patients' quality of life, self-efficacy, and symptom management, pre and post intervention
Inclusion Criteria:	
 • Adult inpatients at Royal Adelaide Hospital and The Queen Elizabeth Hospital in participating units and wards • Sufficient cognitive function and English language skills to be able to provide informed consent and complete assessments. (although interpreters are readily available in the inpatient setting, the main components of this intervention are via telehealth in the transition period after discharge Therefore although we will be able to communicate with the participant's family regarding their care and needs whilst in hospital, interpreter services may not be available via telehealth post-discharge. Also, given that the informed consent form and some written assessments are in English, they need to have adequate English language skills to provide written informed consent). • Ability to engage in telehealth • Presence of multimorbidity defined as :a history of a either diabetes with cardiovascular disease, OR comorbidity in at least 3 of the following illness domains: 
 ○ Diabetes: type 1 or type 2 ○ Cardiovascular disease: symptomatic atherosclerotic disease (ischemic heart disease, cerebrovascular disease, peripheral vascular disease, symptomatic valvular heart disease or

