The aim of this study is to develop and test a transitional model of care to optimally support people living with multimorbidity, post-hospital discharge, via telehealth, and ensure continuity of care between the secondary (acute) and primary healthcare sectors to minimise direct contact with hospital services. We hypothesise that the provision of a transition support service, post-hospital discharge, for patients with multimorbidity will decrease the short-term hospital readmission rate for that patient cohort.

METHODS

Study design and schedule

The study design is a multi-centre pragmatic randomised control trial (pRCT) of patients with multimorbidity. As this is a pRCT, real-world clinical practices, patient flow, and operations will be considerations within the research design elements. A mixed methods approach using quantitative and qualitative data collection methods will be employed. The study setting will be multi-centre, commencing at the Queen Elizabeth Hospital (TQEH), and progressing to the Royal Adelaide Hospital (RAH), Central Adelaide Network (CALHN). Between 3 and 6 medical units and wards will be included.

Randomisation

The randomisation will be at the level of the individual patient. We will go from ward/unit to ward/unit to get the nursing staff to make referrals, but then the patients themselves will be randomised 1:1 to intervention or control. As part of the information provision during the consent discussion, patients will be advised of the randomisation process and its implications.

Participants

The eligible population will be adult inpatients 18 years of age and over that fulfill all inclusion criteria and do not meet any of the exclusion criteria (see Table 1). The patient population was selected as previous work by our team had demonstrated that this population had an approximate 25-30% 28-day readmission rate.

Table 1. Inclusion and exclusion criteria

Inclusion criteria	Exclusion criteria

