Following discharge, the TC will provide transition coordination via telehealth for up to 6 weeks, as indicated by patients' clinical stability. The TC will contact the patient post-discharge at 48 hours, then 1 week later, then 4 weeks later. Clinical assessment by the TC may indicate more frequent phone calls monitoring or intervention are required. During telehealth calls, the TC will review: the TAP, symptoms, appointments attended, medication management, and domestic and health services required/accessed. The TC will undertake appropriate actions (e.g., service referral or follow-up, patient education, liaison with healthcare providers) to coordinate the transition of the patient back to primary care. This will particularly involve liaison with the general practitioner team including the practice nurse involved in the patient's chronic disease care planning. A multidisciplinary case discussion will be held approximately 4- 6 weeks post-discharge between the TC and clinical team.

Handover

The TC holds a final telephone consultation with the patient at 6-10 weeks post-hospital discharge, completes a final assessment, and discharges the patient from the transitional care service. The TC then provides the patient's GP with a letter summarising the issues identified, actions taken, and recommendations for ongoing care.

Outcomes

Primary

- Rate of representation to hospital (emergency department or hospital admission) within 3 months of discharge from index admission

Secondary outcomes

Health care utilisation

- Rate of representation to hospital (emergency department or hospital admission) within 1, 6 and 12 months of discharge from index admission
- Overall length of hospital stay within 1, 3, 6 and 12 months of discharge from index admission
- Cost of transition service model of care

Patient outcomes

- Patient-reported symptom burden
- Patient symptom management/self-efficacy
- Quality of life

- Patient experience, satisfaction, and perceived continuity of care

Organisation of care

- Implementation of components of transitional care model
- Implementation of transition action plan for all patients

Data collection

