The main aim of a sample size calculation will be to determine the number of participants needed to detect a clinically relevant effect of the transitions service intervention. (Charan and Biswas 2013) . As discussed above the patient population has been selected to have a high baseline readmission rate, and these patients are known to have a high proportion of preventable readmissions attributed to poor care coordination. Our previous data has demonstrated that a similar group of patients (those with diabetes and cardiovascular disease (HREC/18/CALHN/120)) have a 25-30% representation rate within 28 days of discharge. As this intervention is anticipated to be up to 6 weeks, and the effect is expected to help prevent representations beyond this time, our primary endpoint will be to evaluate representation to the emergency department or readmission within 3 months.

Our previous study demonstrated that approximately 40% of patients had a representation by 3 months. The readmission rate in this study may be higher due to enrolment of patients with greater multimorbidity, and the exclusion of patients already receiving other CALHN services.

We anticipate that the enrolment of approximately 200 patients over 18 months will be feasible and provide us with sufficient sample size to achieve the primary outcome with the likely baseline readmission rate in the control group and absolute reduction in the intervention group (Table 4). Given that the primary endpoint will be derived from SA health information systems, and the study has an intention-to-treat approach, there will be need to consider a larger sample size for consideration of withdrawals, drop-outs, or loss to follow up.

Table 4. Sample size per group by baseline readmission rate and absolute reduction in readmission with 80% power and $\alpha=0.05$

Absolute reduction in readmission rate in intervention group	Baseline readmission rate in control group at 3 months		
	35%	40%	45%
15%	136	150	160
20%	70	79	86
25%	40	47	52

Statistical methods to be undertaken

An intent-to-treat approach will be used. Linear regression analyses will be conducted to estimate effects of the intervention on primary and secondary outcomes. A hospital fixed effects model will be used to account for stratification at the hospital level. Sensitivity analyses will be performed to assess the robustness of the findings.

DATA SECURITY AND HANDLING

Data management and storage

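### The synopsis gives 1-month readmission as the primary objective, but the Outcomes and sample size sections make 3-month ED presentation or admission the primary endpoint

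*Protocol*

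**What the plan says.** - **Synopsis, Primary Objectives.** One item only: "Assess impact of intervention on 1 month readmission" after discharge.
- **Outcomes, Primary.** One item only: "Rate of representation to hospital (emergency department or hospital admission) within 3 months of discharge from index admission".
- **Secondary outcomes, Health care utilisation.** The 1-month time point appears here: "Rate of representation to hospital (emergency department or hospital admission) within 1, 6 and 12 months of discharge from index admission".
- **Sample size estimation & justification.** "our primary endpoint will be to evaluate representation to the emergency department or readmission within 3 months". The reason given is that the intervention may last up to 6 weeks and should prevent events after that. The control rate comes from an earlier study in which "approximately 40% of patients had a representation by 3 months". Table 4 uses 3-month control rates of 35%, 40% and 45%.
- **Aim and Hypothesis.** The service "will decrease the short-term hospital readmission rate for that patient cohort". No time point is attached.
- **28-day rate.** The sample size section says that similar patients "have a 25-30% representation rate within 28 days of discharge". Methods, Participants gives the same 25-30% but calls it a readmission rate.

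No section reconciles the synopsis with the rest.

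**The concern.** A confirmatory trial rests its conclusion on one endpoint fixed in advance. Here the synopsis fixes one and the body fixes another. They differ in time point (1 month against 3 months) and, as worded, in event (readmission against ED presentation or admission). If the two gave different results, the protocol would offer written support for reporting either one as primary, which is the latitude that pre-specification is meant to remove.

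The second consequence concerns the sample size. If the synopsis governed, the plan would contain no calculation for its primary endpoint, and that endpoint would close before the end of an intervention that can run to 6 weeks. The second of these is the protocol's own argument for choosing 3 months.

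**Working it through.** **Step 1. The statements side by side (protocol).**

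| Section | Time point | Event as worded | Status |
|---|---|---|---|
| Synopsis, Primary Objectives | 1 month | readmission | primary |
| Outcomes, Primary | 3 months | ED presentation or admission | primary |
| Secondary outcomes | 1, 6, 12 months | ED presentation or admission | secondary |
| Sample size section | 3 months | ED presentation or readmission | primary |
| Aim and Hypothesis | short-term, unspecified | readmission | not ranked |

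The 1-month time point is primary in one place and secondary in another. The hypothesis fits either reading.

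**Step 2. Reproduce Table 4.** Inputs: 80% power, alpha 0.05 (sidedness is not stated; two-sided reproduces the table), 1:1 allocation, control rates 35/40/45%, absolute reductions d of 15/20/25 points. Two-proportion normal approximation, unpooled variance, no continuity correction:

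n per arm = (1.96 + 0.8416)² × [p1(1−p1) + p2(1−p2)] / d²

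Example, 40% to 20%: 7.849 × (0.24 + 0.16) / 0.04 = 78.5, rounded up to 79, as stated.

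| Reduction | 35% | 40% | 45% |
|---|---|---|---|
| 15 points | 136 | 150 | 160 |
| 20 points | 70 | 79 | 86 |
| 25 points | 40 | 47 | 52 |

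All nine cells match. All use 3-month rates, and none uses the 28-day rate of 25-30%. The table supports only the 3-month endpoint.

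**Step 3. Power with 100 per arm (200 planned, 1:1) at each time point.** Same approximation:

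power = Φ( d / √{[p1(1−p1) + p2(1−p2)] / 100} − 1.96 )

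The control rate is 40% at 3 months and 25-30% at 1 month (the 28-day figure). The protocol gives no 1-month target effect, so the 1-month effects below are assumptions, shown on both scales.

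| Assumed effect | 3 months, 40% | 1 month, 25% | 1 month, 30% |
|---|---|---|---|
| Risk halved | to 20%: 88.5% | to 12.5%: 63% | to 15%: 73% |
| 20-point reduction | to 20%: 88.5% | to 5%: 98% | to 10%: 95% |
| 15-point reduction | to 25%: 63% | to 10%: 81% | to 15%: 73% |

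Example, 25% to 12.5%: 0.125 / √[(0.1875 + 0.109375) / 100] = 0.125 / 0.05449 = 2.294; Φ(2.294 − 1.96) = 0.63.

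A pooled-variance test gives almost the same picture: 62-72% for halving and 95-98% for 20 points at 1 month, against 88% at 3 months.

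On a constant relative effect, 1 month has less power. On the absolute scale that Table 4 uses, it has more. The direction depends on the assumption.

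**The case against.** The strongest reply is that every operative section agrees. Outcomes lists one primary outcome and ranks 1 month as secondary. The sample size section names and justifies 3 months, and Table 4 follows. On this view a single synopsis line is out of step. That is a fair description, and it makes the correction easy, but it does not remove the contradiction: the synopsis is current text, and nothing says that the body takes precedence.

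Three stronger readings are tempting, and the documents do not support them.

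- *The trial has two primary endpoints, so its 5% error rate is broken.* No co-primary endpoints are declared. Inflation would require someone to switch endpoints after seeing the data, against a body text that ranks 1 month as secondary. The inconsistency weakens protection against that; it does not show that it will happen.
- *The trial is underpowered at 1 month.* This holds if the risk is halved and fails for a 20-point reduction. Halving may be the more plausible assumption, since a 20-point reduction means cutting 25-30% to 5-10%, but the protocol specifies neither effect at 1 month.
- *The 28-day figure counts ED presentations too, so readmission alone would be rarer and power worse still.* The protocol calls the same 25-30% a readmission rate in Methods, Participants and a representation rate in the sample size section. Table 4 likewise labels its control rates as readmission after a text that derives 40% from representations. The terms are used interchangeably, so the difference in event may be loose wording, and no inference about power can rest on one of the two labels.

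**Conclusion.** The point stands as an internal contradiction about the single primary endpoint: 1-month readmission in the synopsis, 3-month ED presentation or admission in the Outcomes and sample size sections. The difference in time point is unambiguous; the difference in event is certain only as wording. The protocol's own rationale and all nine cells of Table 4 belong to the 3-month endpoint, so the synopsis is the text to correct.

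Two consequences hold: weaker protection against choosing the endpoint after the data are seen, and no sample size calculation for a 1-month primary. A reader might also infer a loss of power at 1 month. With 100 per arm the figures run from 63-73% (risk halved) to 95-98% (20-point reduction), against 88.5% at 3 months, so no such loss is established. These figures assume two-sided alpha 0.05, the normal approximation, and the protocol's control rates of 25-30% and 40%.

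It should be corrected before outcomes are examined by arm, because the primary endpoint determines what the trial can conclude.

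**What to change.** 1. In the synopsis, restate the primary objective as the effect of the intervention on representation (ED presentation or hospital admission) within 3 months of discharge from the index admission.
2. Keep the 1-month measure as a secondary outcome only, as the Outcomes section already has it.
3. State the 3-month time point in the hypothesis in place of the unspecified short term.
4. Choose one term for the event and use it in the study question, the hypothesis, Methods (Participants), the sample size text and the labels of Table 4. State once what the earlier 25-30% and 40% figures counted.

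The cost is a wording amendment, carried into any ethics text that repeats the synopsis objective. No extra patients or data are needed, and the numbers in Table 4 and the planned total of 200 are not affected by this correction.

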- g) *In case the results have significance for the participants' welfare there is, where practicable, a plan for making information arising from the research available to them (for example, via a disease-specific website or regional news media)*

Response: Patients who are screened and found to be ineligible for the study will not be followed up in any way. Any documentation or listing of these patients' details (documentation will be on paper) will be discarded through the confidential bins when no longer needed. Information will be made available to patients consenting to and taking part in the research, as discussed in section 'Dissemination of program

outcomes’.

- h) *The possibility of commercial exploitation of derivatives of the data or tissue will not deprive the participants of any financial benefits to which they would be entitled*

Response: There will be no entitlement for these patients, as they are not participating in the research and their details will be confidentiality discarded (following discernment of ineligibility during the screening process).

- i) *The waiver is not prohibited by State, federal, or international law.*

Response:

The consent waiver being applied for is only applicable at the point of screening for study eligibility and is not prohibited by State, federal, or international law.

Data access

Access to participants medical record will require accessing data through Sunrise. Table 2 below lists the data source, software and related information to be accessed as part of the study.

Table 2. Access to existing data

Access to existing data table	
Name/Description of data	CALHN Electronic Medical Records
Data Custodian	CALHN
Database Name	Sunrise
Agency Type	State
Data Collection Format	Identifiable

Intervention

The intervention involves a transitional care service, based on the transition care model developed by Naylor and colleagues.^(17,18) The intervention components were informed by the following: literature on transitional care; the study team’s prior experience in delivering nurse-led models of care for people with multimorbidity; previous consumer/participant feedback from the feasibility study; and, the Foundations Framework for developing and reporting models of care for multimorbidity.⁽¹⁹⁾ The intervention will be provided by registered nurses referred to as Transition Coordinators (TCs). The TC’s role is supported by Naylor’s transitional model, which requires the provision of:

a broad range of time-limited services designed to ensure health care continuity, avoid preventable poor outcomes among at-risk populations, and promote the safe and timely transfer of patients from one level of care to another or from one type of setting to another.⁽²⁰⁾

Each participant in the study will have a ‘primary transition coordinator’ who will have responsibility to provide care coordination and continuity of care for that participant’s transition. However, the information will be carefully documented and handed over in case of unavailability of the primary transition coordinator, to a ‘secondary transition coordinator’.

Transition care coordination involves three stages: inpatient baseline assessment, risk of readmission and transition planning, transitional care coordination, and handover to the general practitioner. Successful transition coordination requires that when patients are discharged from hospital General Practitioners (GPs) are notified (phone call) within 24 hours of discharge, and an appointment made for patient review in a timely manner. It will be the TCs responsibility to provide the GP with information regarding the time critical nature of the appointment. We will test this as part of our intervention. Figure 1 represents the intervention components,

aligned to the key areas in Stokes' framework: clinical focus, organisation of care delivery, and support for model delivery.

[figure not shown]

Figure 1. The intervention components, aligned to the key areas in Stokes' framework.

Baseline assessment and planning

At baseline, the TC will assess the participant demographics, frailty, activities of daily living, cognitive function, depression and anxiety, mobility, health literacy, medication management, comorbidities, nutrition, end-of-life planning, and risk of re-hospitalisation. Next, the TC will develop a Transition Action Plan (TAP) with the patient, identifying services required on discharge (e.g., meals assistance, medication review, psychology). The TAP will be reviewed with the patient prior to discharge, entered into the patient's medical notes, and communicated to the GP (within 24 hours of discharge). The TC will ensure a post-discharge GP appointment within 2 weeks of discharge, preferably within the first week, and organize a home medication review if appropriate. The process of transition patient assessment, care planning and communication is anticipated to take between 2 and 3 hours. Within the research context, the assessment and planning time are fundamental in establishing a therapeutic, sensitive, and trusting relationship between the TC and patient, without burdening the patient. The patient will be provided with the choice to self-select the technology used for communication. The post-hospital discharge care coordination follow

up appointments will be via Telehealth, using telephone, or iPad/app (provided). If the patient self-selects 'iPad/app', technology training and support will be provided, and the technology and process trialled in hospital, prior to discharge. Telehealth appointments will be conducted using the HealthDirect app, which is used across SA health for video telehealth consultations and supported by SA Health ICT services. Given that HealthDirect is already used by SA Health it has all of the necessary security and confidentiality requirements for the purpose of video telehealth consultations. There will be no video or audio data recorded as part of the telehealth consultations hence there are no anticipated issues regarding data storage and security.

Transitional care coordination

Following discharge, the TC will provide transition coordination via telehealth for up to 6 weeks, as indicated by patients' clinical stability. The TC will contact the patient post-discharge at 48 hours, then 1 week later, then 4 weeks later. Clinical assessment by the TC may indicate more frequent phone calls monitoring or intervention are required. During telehealth calls, the TC will review: the TAP, symptoms, appointments attended, medication management, and domestic and health services required/accessed. The TC will undertake appropriate actions (e.g., service referral or follow-up, patient education, liaison with healthcare providers) to coordinate the transition of the patient back to primary care. This will particularly involve liaison with the general practitioner team including the practice nurse involved in the patient's chronic disease care planning. A multidisciplinary case discussion will be held approximately 4- 6 weeks post-discharge between the TC and clinical team.

Handover

The TC holds a final telephone consultation with the patient at 6-10 weeks post-hospital discharge, completes a final assessment, and discharges the patient from the transitional care service. The TC then provides the patient's GP with a letter summarising the issues identified, actions taken, and recommendations for ongoing care.

Outcomes

Primary

- Rate of representation to hospital (emergency department or hospital admission) within 3 months of discharge from index admission

Secondary outcomes

Health care utilisation

- Rate of representation to hospital (emergency department or hospital admission) within 1, 6 and 12 months of discharge from index admission
- Overall length of hospital stay within 1, 3, 6 and 12 months of discharge from index admission
- Cost of transition service model of care

Patient outcomes

- Patient-reported symptom burden
- Patient symptom management/self-efficacy
- Quality of life

- Patient experience, satisfaction, and perceived continuity of care

Organisation of care

- Implementation of components of transitional care model
- Implementation of transition action plan for all patients

Data collection

Data collection will require the collection of patient assessment and medical record data, as well as questionnaire responses. Figure 2 depicts the data collection required at certain time points (e.g., in-patient screening, through to 3-month discharge from the transition service and follow up surveys). Table 3 provides details on the data collection tools. Again, the TC will be sensitive to the patient, continuing rapport thought the research, without burdening the patient.

Table 3. Data collection instruments, purpose, and validation

Instrument	Primary use/purpose	No. of items
Patient Continuity of care questionnaire (PCCQ)	PCCQ measures patient perceptions of factors central to continuity of care. The questionnaire subscales correspond to the theoretical components of continuity of care that have been proposed in the literature, namely informational, relational and management continuity.	41
Edmonton Symptom Assessment System – Revised (ESAS-r)	The ESAS-r assesses symptom burden.	9
EQ5D3L	EQ5D3L is a preference-based measure of health status that assesses patient experience of health at a point in time, for clinical, population, health and economic evaluation surveys.	5

[figure not shown]

Figure 2. Time points (TP) aligned with data collection, phone calls, interventions, and other relevant details

PARTICIPANT SAFETY AND WITHDRAWAL

Risk management and safety

Involvement in the research carries no more than low risk.

Involvement in the research carries no more than low risk because there is no anticipated harm or discomfort for participants associated with taking part. However, there are four possible low/minor risks, including:

1. TCs or [name] accessing potential patients' medical information during the screening process for participant eligibility, without their prior consent (thus this waiver for consent at this point).
2. The additional contact and healthcare interactions which the patients receive as part of the care transition service.
3. The conduct of the questionnaires and the inconvenience and discomfort associated with answering the questions.
4. The potential for creating dependency in the relationship between the TC and participant.

There is no anticipated harm or discomfort associated with taking part in this research. However, the four possible minor risks listed above will be mitigated in the following ways. The first risk will be managed through SA Health permission to waive consent for this procedure (for rationale -see above). Secondly, the additional or new and ongoing home/healthcare services the patient receives during the transition intervention will be provided through professional health support services. The patient will not be exposed to any additional risk other than that which people would normally incur when routinely accessing these services. The other anticipated inconvenience is tiring during assessment, or questionnaire completion. Patients will be offered breaks and comfort rests where appropriate.

Lastly, the patient and TC relationship will be established as a collaborative one throughout the intervention. To initially affirm the patient's agency, the transition action plan will be developed collaboratively with the patient. Part of the study is to enable patients' self-efficacy, and this will be achieved through education, support and coaching during phone calls, along with decreasing support and phone calls as the intervention progresses, and the patient's independence increases. Lastly, patients' will be prepared for completion of the intervention, through collaborative discussion and agreement of their transition discharge status and the communication and handover of this to their GP and Practice nurse. When discharged from the transition service, patients will not be left without support, but ongoing healthcare and supports will be coordinated through their primary healthcare provider.

The benefits from the research justify any risks of harm associated with not seeking consent.

The benefits include minimising unnecessary contact, potential interactions, stress or confusion with patients, as well as not wasting patients' time. These interactions maybe unnecessary, because during the 'screening for eligibility process' a majority of patients will be found to be ineligible (this was the case in the feasibility study).

It is impracticable to obtain consent, and the rationales for this are addressed below including the following points:

- ▶ Why is it impractical to gain consent?
- ▶ Time period
- ▶ How many records will be accessed?
- ▶ Are there limitations to resources?
- ▶ Mortality rates
- ▶ Lost to follow up

It is impracticable to obtain consent at this point in the research because of the volume of patients required to screen each day, and the additional time and cost this would take for the researchers. The additional time and cost would not contribute to improved ethical outcomes; therefore, the additional time would be unnecessary, inordinate and preclude meeting study timelines. Impracticability of obtaining consent particularly relates to the quantity of patient medical records that require scrutiny during the screening for eligibility. The age of patients is an issue as far as some may be quite elderly or frail and additional unnecessary contact with researchers could be stressful. The accessibility of records is not an issue, however the limitations to resources, is an issue as stated above, the additional time required would be unjustifiably costly. The mortality rate of participants will not be affected and the inability to contact participants due to access to contact details or due to likelihood of contact details having changed due to time or due to characteristics of participant groups, is irrelevant.

There is no known or likely reason for thinking that participants would not have consented if they had been asked.

There is no known or likely reason for thinking that participants would not have consented if they had been asked, however as discussed above, obtaining consent is impracticable.

There is sufficient protection of their privacy.

To protect the patient's privacy the details of the participants who are accessed will be documented on paper, then will be discarded through the confidential bins when no longer needed.

In case the results have significance for the participants' welfare there is, where practicable, a plan for making information arising from the research available to them (for example, via a disease-specific website or regional news media).

Patients who are screened and found to be ineligible for the study will not be followed up in any way. Any documentation or listing of these patients' details (documentation will be on paper) will be discarded through the confidential bins when no longer needed. Information will be made available to patients consenting to and taking part in the research, as discussed in section titled 'Dissemination of program outcomes', page 22. However, information will be made available to patients consenting to and taking part in the research, as discussed in the section headed

The possibility of commercial exploitation of derivatives of the data or tissue will not deprive the participants of any financial benefits to which they would be entitled.

There will be no entitlement for these patients, as they are not participating in the research and their details will be confidentiality discarded (following discernment of ineligibility during the screening process).

The waiver is not prohibited by State, federal, or international law.

The consent waiver being applied for is only applicable at the point of screening for study eligibility and is not prohibited by State, federal, or international law.

Protocol deviations

A 'serious breach' is a breach of Good Clinical Practice or a breach of the protocol that is likely to affect to a significant degree the safety or rights of a trial participant, or the reliability and robustness of the data generated in the clinical trial. The principal investigator will use continuous vigilance to identify and report any suspected breaches to the sponsor within 72 hours of becoming aware of the event and report any serious breaches confirmed by the sponsor as occurring at the site to their institution (research governance office) within 72 hours of being notified of the serious breach.

Handling of withdrawals

Patients are free to withdraw from the project at any time, or for any reason, or the investigator deems it is in the participant's best interest to do so. If they do withdraw consent during the research project, any personal information already collected will be retained to ensure that the results of the research project can be measured properly and to comply with law. Patients will be advised that data collected by the study team up to the time of withdrawal will form part of the research project results. The patient's readmission data will also be collected from SA health information systems for the trial's primary endpoint. All information will be managed in compliance with the Australian Code for the Responsible Conduct of Research (2018), the University of South Australia ownership and retention of data policy and a created data management plan in line with UniSA procedure requirements.

ANALYSIS

Sample size estimation & justification

The main aim of a sample size calculation will be to determine the number of participants needed to detect a clinically relevant effect of the transitions service intervention. (Charan and Biswas 2013) . As discussed above the patient population has been selected to have a high baseline readmission rate, and these patients are known to have a high proportion of preventable readmissions attributed to poor care coordination. Our previous data has demonstrated that a similar group of patients (those with diabetes and cardiovascular disease (HREC/18/CALHN/120)) have a 25-30% representation rate within 28 days of discharge. As this intervention is anticipated to be up to 6 weeks, and the effect is expected to help prevent representations beyond this time, our primary endpoint will be to evaluate representation to the emergency department or readmission within 3 months.

Our previous study demonstrated that approximately 40% of patients had a representation by 3 months. The readmission rate in this study may be higher due to enrolment of patients with greater multimorbidity, and the exclusion of patients already receiving other CALHN services.

We anticipate that the enrolment of approximately 200 patients over 18 months will be feasible and provide us with sufficient sample size to achieve the primary outcome with the likely baseline readmission rate in the control group and absolute reduction in the intervention group (Table 4). Given that the primary endpoint will be derived from SA health information systems, and the study has an intention-to-treat approach, there will be need to consider a larger sample size for consideration of withdrawals, drop-outs, or loss to follow up.

Table 4. Sample size per group by baseline readmission rate and absolute reduction in readmission with 80% power and $\alpha=0.05$

Absolute reduction in readmission rate in intervention group	Baseline readmission rate in control group at 3 months		
	35%	40%	45%
15%	136	150	160
20%	70	79	86
25%	40	47	52

Statistical methods to be undertaken

An intent-to-treat approach will be used. Linear regression analyses will be conducted to estimate effects of the intervention on primary and secondary outcomes. A hospital fixed effects model will be used to account for stratification at the hospital level. Sensitivity analyses will be performed to assess the robustness of the findings.

DATA SECURITY AND HANDLING

Data management and storage

